6.7.4 Rescue medicine

Rescue topical medications use will be at the discretion of the Investigator after discussion with the Medical Monitor if the patient is flaring above 14% treatable BSA (excluding scalp, palms, soles and genitalia) during the last two weeks of the Open Label Period. Investigators should make every attempt to conduct efficacy and safety assessments (eg, disease severity scores, safety labs) immediately before administering any rescue treatment. An unscheduled visit may be used for this, if necessary. Patients who receive rescue treatment will be asked to continue with study treatment and procedures.

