9.4.3 Analysis of efficacy data

Efficacy analyses will be based on the Efficacy population. A patient will be considered evaluable per endpoint and study period, if they receive at least 80% of prescribed study intervention in that period and have a post-baseline assessment of the corresponding endpoint for that period (ie, after Day 1 or after Day 15).

Where appropriate, supplemental analyses will be presented excluding observations after administration of rescue medication. Imputation would then be performed for missing observations including those due to withdrawal due to lack of efficacy, as will be specified in the SAP.

Efficacy analyses will be an early explorative assessment and performed without the aim of formal inferential statistics. No adjustment will be made for multiple analyses.

Treatment differences or ratios will be assessed for PRN473 Gel, 5% versus placebo, mainly at Day 15. Data will be presented by treatment for the Blinded Period where assessed per lesion, and overall otherwise, as well as for the Open-Label Period.

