 - Proportion of participants with at least a reduction $\geq 50\%$ in EASI (EASI-50), with at least a reduction $\geq 75\%$ in EASI (EASI-75), with at least a reduction $\geq 90\%$ in EASI (EASI-90), and with at least a reduction $\geq 100\%$ in EASI (EASI-100), from Baseline to Days 15, 29 and 43
 - Proportion of participants with EASI-50, EASI-75, EASI-90, and EASI-100 from Day 15 to Days 29 and 43
- For v-IGA-AD
 - Proportion of participants achieving vIGA-AD of 0 (clear) or 1 (almost clear) at Day 29

- Proportion of participants achieving a vIGA-AD of 0 (clear) or 1 (almost clear) at Day 43
- Proportion of participants achieving vIGA-AD of 0 (clear) or 1 (almost clear) and a reduction of ≥ 2 points from Day 15 to Day 29
- Proportion of participants achieving vIGA-AD of 0 (clear) or 1 (almost clear) and a reduction of ≥ 2 points from Day 15 to Day 43
- For Body Surface Area (BSA)
 - Change from Day 15 in percentage of treatable BSA at Days 29 and 43
- For Scoring Atopic Dermatitis (SCORAD)
 - Percent change from Day 15 in SCORAD index at Days 29 and 43
- For Patient Oriented Eczema Measure (POEM)
 - Change from Baseline in POEM at Days 15, 29, and 43
 - Change from Day 15 in POEM at Days 29 and 43
 - Proportions of participants with a reduction in POEM ≥ 4 from Baseline at Days 15, 29 and 43 in participants with POEM ≥ 4 at Baseline
 - Proportions of participants with a reduction in POEM ≥ 4 from Day 15 at Days 29 and 43 in participants with POEM ≥ 4 at Day 15
- For Dermatology Quality of Life Index (DLQI)
 - Change from Baseline in DLQI at Days 15, 29, and 43.
 - Change from Day 15 in DLQI at Days 15, 29, and 43
 - Proportions of participants with a reduction in DLQI ≥ 4 from Baseline at Days 15, 29 and 43 in participants with DLQI ≥ 4 at Baseline
 - Proportions of participants with a reduction in DLQI ≥ 4 from Day 15 at Days 29 and 43 in participants with DLQI ≥ 4 at Day 15

Analyses for binary endpoints

The binary endpoints will be descriptively summarized using number, percentage and 95% confidence interval (CI) of percentage at each time point.

The proportion of subjects meeting the binary endpoint during the Open label period and corresponding exact 95% and 80% CI (95% CI and 80% CI respectively calculate with Wilson score method) will be summarized.

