Participants with missing data at Baseline will not be included in the analysis. Participants with one or more post-dose timepoints will be included. Mixed model for repeated measures (MMRM) to account for missing data is used for the primary analysis under the missing at random (MAR) framework. Parameters will be estimated using restricted maximum likelihood method with the Newton-Raphson algorithm. Denominator degrees of freedom will be estimated using Kenward-Roger adjustment. All efficacy data after discontinuation of treatment will not be considered.

The same analysis will be conducted for lesional v-IGA-AD score at Days 8 and 15 and lesional PP-NRS. For the other efficacy parameters, only descriptive analyses will be provided.

The weekly average PP-NRS scores will be defined as the average of daily non-missing scores within the week preceding the given visit and will be calculated if there is a minimal amount of 4 non-missing scores.

The POEM score is a 5-point scale: 0 (“No days”), 1 (“1-2 days”), 2 (“3-4 days”), 3 (“5-6 days”) and 4 (“Every day”). The POEM score is calculated by summing the values for the 7 items.

If two or more questions are left unanswered the questionnaire is not scored.

The DLQI is a 4-point scale: 0 (“Not relevant”/“Not at all”), 1 (“A little”), 2 (“A lot”), 3 (“Very much”). For Question 7, “Prevented work or studying” is scored at 3. The DLQI is calculated by summing the score of each question.

The EASI-50/75/95/100 response is defined as a participant achieved a decrease by at least 50%/ 75%/ 95%/100% of EASI from Day 15.

Change in lesional TSS, PP-NRS (daily global and weekly average), EASI, BSA, SCORAD, POEM, DLQI during the Open label period will be analyzed descriptively. Estimations with 95% and 80% CIs may be derived. Sub-score of EASI by localization will also be provided.

Supplemental analyses

Where appropriate, supplemental analyses may be presented excluding observations after administration of rescue medication. No imputation will be made.

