3.9 CHANGES TO PROTOCOL-PLANNED ANALYSES

No major statistical changes were included in the protocol amendment(s).

One major statistical change in SAP to the current amended protocol has been made and is summarized in the section below:

Major statistical changes in SAP to (current) amended protocol

Current Amended Protocol Number	Section	Changes	Rationale
	2- Analysis Populations	Delete ITT population Redefine Efficacy population	ITT population is not used in the analysis Efficacy population has been redefined to take into account compliance during both periods (double-blind and open-label period)

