5.4 APPENDIX 4 DATA HANDLING CONVENTIONS

Double blind analysis period is defined from the date of first IMP up to Day15 or date of IMP discontinuation which ever comes first.

Day15 of Open label period is defined as the first day the placebo is not used.

For parameters with evaluations before administration and in cases of rechecked value(s) for one participant, only the last observation will be used as baseline in descriptive statistics and derivations of other parameter values. After baseline, only observations planned in the protocol will be used in descriptive statistics.

For clinical laboratory parameters with non-numeric values, the imputed values used for the descriptive statistics and/or the flags will be determined by considering the following rules:

- If database value is ‘<X’, the value used will be X/2
- If database value is ‘>X’, the value used will be X
- If database value is a range (eg, ‘X – Y’), the values used will be (Y + X)/2

Pharmacokinetic analysis

For ease of presentation, mean values will be arithmetic mean unless specified. Concentration values below the plasma assay limit will be treated as zero in all summary statistics. Mean values below LLOQ will be reported as LLOQ in the tables and not plotted in the figures if after maximal plasma concentration (C_{max}). Mean calculations and their associated statistics will be generated from unrounded numbers and may differ slightly from those values that would be determined using the rounded numbers displayed in the tables. Values expressed in all tables will before ease of presentation and will not be meant to imply accuracy to more than 3 significant figures.

Area under the curve (AUC) values extrapolated by more than 30% will be excluded from any pharmacokinetic statistical analysis.

Analysis windows for time points

The following analysis windows will decide how the scheduled and/or unscheduled visits will be used in the by-visit analyses of efficacy. For participants with premature study discontinuation, follow-up measurements will be reallocated to the corresponding analysis window and reported together with other measurements.

A measurement (scheduled or unscheduled) will be used if it is available and measurement date is within the analysis window.

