After applying these time windows, if multiple assessments are associated to the same time point, the closest from the targeted study day will be used. If the difference is a tie, the value after the targeted study day will be used. If multiple valid values exist within a same day, then the first value of the day will be selected when time is available, otherwise the scheduled exam will be used.

If there is no measurement for a given parameter in an analysis window, data will be considered missing for the corresponding visit.

Table 6 - Analyses window definition

Study period	Scheduled visit post baseline	Targeted study day	Analysis window in study days
Double blind period	Day 8	8	7 to 9
	Day 15	15	13 to 18
Open label period	Day 29	29	25 to 33
	Day 43	43	39 to 47

Study days are calculated considering Day 1 as the day of first administration of intervention in blinded period.

Unscheduled and end of treatment (EOT)/EOS visits

Unscheduled visit measurements of efficacy, laboratory data, vital signs, PK and biomarkers will be used, in particular for computation of Baseline, the last on-treatment value, analysis according to PCSAs, and the shift summaries for safety. They will also be included in the by-visit summaries if they are re-allocated to scheduled visits.

Signature Page for VV-CLIN-0634985 v1.0
act17131-16-1-9-sap

Approve & eSign

Approve & eSign

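### SAP 3.4 withdraws the imputation that Protocol 9.4.3 promised for the rescue-excluded efficacy analysis, and SAP 3.9 does not declare the change

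*SAP*

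**What the plan says.** Protocol 9.4.3 plans, where appropriate, supplemental efficacy analyses that drop observations made after rescue. It says that they *will* be presented and adds: "Imputation would then be performed for missing observations including those due to withdrawal due to lack of efficacy". The specification is deferred to the SAP.

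The corresponding text in SAP 3.4 keeps the where-appropriate condition but reads: "supplemental analyses may be presented excluding observations after administration of rescue medication. No imputation will be made".

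SAP 3.9 states that "One major statistical change in SAP to the current amended protocol has been made". The change it tabulates is the deletion of the ITT population and the redefinition of the Efficacy population. Neither rescue nor imputation appears there.

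Protocol 6.7.4 confines rescue to patients flaring "during the last two weeks of the Open Label Period" and adds: "Patients who receive rescue treatment will be asked to continue with study treatment and procedures".

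Three SAP rules decide what happens to a rescued patient's Day 43 result:

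- SAP 5.4, analysis windows: "If there is no measurement for a given parameter in an analysis window, data will be considered missing for the corresponding visit". The Day 43 window runs from Day 39 to Day 47.
- SAP 5.4, data handling: "After baseline, only observations planned in the protocol will be used in descriptive statistics". The windows text in the same appendix, however, admits unscheduled measurements.
- SAP 3.4, binary endpoints: "The proportion of subjects meeting the binary endpoint during the Open label period and corresponding exact 95% and 80% CI" will be summarized, with intervals by the Wilson score method. Nothing is said about participants with no value at the visit.

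**The concern.** The protocol left open how to impute, not whether to. The SAP states that it is based on Amended Protocol 02, which contains the imputation sentence, so this is not a difference between protocol versions.

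The patients concerned are not a random subset. They were rescued because they flared above 14% treatable BSA, or they withdrew because the gel was not working, so most would be expected to be non-responders. Removing their post-rescue scores and putting nothing in their place turns probable failures into missing values. If missing participants are then left out of the denominator, the Day 43 proportions for EASI-50/75/90/100, vIGA-AD 0/1 and the PP-NRS responses tend to rise. The open-label period has no placebo arm against which such a shift would show. Because the denominator is not stated, two programmers could also report different rates from the same data.

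**Working it through.** The plan gives no response rate, rescue rate or sample-size calculation, so there is no figure to reproduce. The check has three parts.

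**1. The texts side by side**

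| Item | Protocol 9.4.3 | SAP 3.4 | In SAP 3.9? |
|---|---|---|---|
| Condition | where appropriate | where appropriate | unchanged |
| Presentation | will | may | no |
| Imputation | to be performed, method in SAP | none | no |

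The imputation row is a reversal. The presentation row is a softening under an unchanged condition.

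The mixed model in SAP 3.4, which assumes data missing at random, does not fill the gap. It covers the lesional comparison of gel and placebo in the blinded period. Rescue is foreseen only later, where the analyses are descriptive.

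**2. When a rescued patient becomes missing at Day 43**

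- Open-label dosing is Days 15-42, so its last two weeks are Days 29-42: 42 − 29 + 1 = 14 days.
- The Day 43 window opens on Day 39. A score taken before rescue can fall in it only if rescue starts on Day 39 or later.
- Rescue on Days 29-38 therefore leaves no usable Day 43 score: 38 − 29 + 1 = 10 days, and 10/14 = 71% of the possible rescue days.
- For rescue on Days 39-42, a visit-based score depends on an unscheduled pre-rescue assessment. If the planned-observations sentence in SAP 5.4 bars it, those days are lost too.

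The 71% is a share of days. It is a share of rescued patients only if rescues are spread evenly.

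**3. Size of the effect (all counts assumed)**

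Let x be the responders, n = 40 the participants in the open-label efficacy population, and f the rescued participants who leave the denominator. No rescued participant is a responder.

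Counted as non-responders: x/n. Dropped: x/(n − f).

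| x | x/40 (80% Wilson CI) | f = 2 | f = 4 | Largest shift, points |
|---|---|---|---|---|
| 6 | 15.0% (9.2-23.6) | 15.8% | 16.7% | 1.7 |
| 12 | 30.0% (21.7-39.9) | 31.6% | 33.3% | 3.3 |
| 18 | 45.0% (35.3-55.1) | 47.4% | 50.0% | 5.0 |

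For the middle row: 12/40 = 30.0%, 12/38 = 31.6%, 12/36 = 33.3%, and 33.3 − 30.0 = 3.3 points. The 95% Wilson interval for 12/40 is 18.1-45.4%. With f = 0 the shift is zero in every row. Every shifted rate lies inside the 80% interval of its unshifted rate.

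**The case against.** The strongest reply concerns weight. No hypothesis is tested, the protocol calls the study signal seeking, and the affected item is a conditional supplement to exploratory, uncontrolled endpoints. SAP 3.9 is framed around major changes, and the sponsor may regard this one as minor. That limits the consequence. It does not remove the contradiction: the same table finds room to record the deletion of a population that the SAP says is not used.

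The second reply is that the inflation may never occur. SAP 3.4 bases the efficacy endpoints on the efficacy population. If that population is the denominator, a rescued patient with no Day 43 value stays in it and the rate does not move. Protocol 9.4.3 leans the same way, since one post-baseline assessment in the period makes a patient evaluable, and someone rescued after the Day 29 visit normally has one. This stands as a possible reading, but the SAP does not state it.

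A reader might also infer more than the documents support:

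- *That the protocol promised non-responder imputation.* It promised imputation without naming a method.
- *That withdrawals for lack of efficacy add to the shift.* Adding 2 of them to the 4 rescued gives 12/34 = 35.3%, or 5.3 points. But the open-label efficacy population requires at least 80% of prescribed drug. On a full-course reading that is 0.80 × 56 = 44.8, so 45 doses, reached about Day 37; earlier withdrawals are then outside the population under either document. Under SAP 3.6.1, which counts compliance to the last actual dose, they could stay in. The figure is therefore not clearly a protocol-to-SAP difference.
- *That the reported efficacy results are biased.* The Day 15 comparison precedes any foreseen rescue, and the main open-label summaries keep post-rescue data.

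**Conclusion.** The concern holds in a limited form. SAP 3.4 reverses a stated commitment to impute, and SAP 3.9 does not declare it. That part rests on the text alone and is firm. The change from *will* to *may* is secondary.

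The bias is conditional. It requires at least one participant rescued, or withdrawn for lack of efficacy and still in the efficacy population; a Day 43 value made missing; and a denominator that drops that participant. When all three hold, the supplemental rates are likely, though not certain, to be too high. The shift is up to 3.3 points for 12 responders of 40 with 4 rescued, and 1.7 to 5.0 points for 6 to 18 responders. These counts are assumptions, and the shifts are small beside the sampling error. The point deserves correction because the rule is undeclared and the denominator undefined, not because the effect is large.

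**What to change.** In SAP 3.4, replace the no-imputation sentence with a rule limited to the rescue-excluded supplemental analysis:

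- **Binary open-label endpoints.** Participants in the open-label efficacy population who were rescued or withdrew for lack of efficacy count as non-responders at every later visit (Day 29 or Day 43, as applicable) and stay in the denominator.
- **Continuous endpoints.** Specify the imputation that Protocol 9.4.3 promised, or list its removal in SAP 3.9 with a reason.
- **Declaration.** Record in SAP 3.9 any remaining departure from Protocol 9.4.3, including *may* in place of *will* if that is kept.

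Leave the 80% compliance criterion as it is. Overriding it to retain early withdrawals would go beyond either document. The main summaries stay as planned.

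The cost is SAP wording and one derivation flag, plus the programming of an imputation for continuous endpoints if that option is chosen. The supplemental responder rates may come out slightly less favourable.

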3.5 MULTIPLICITY ISSUES

No adjustment will be made for multiple analyses.

3.6 SAFETY ANALYSES

All safety analyses will be performed on the safety population as defined in [Section 2](#), during double blind and Open-label period separately and overall unless otherwise specified, using the following common rules:

- The analysis of the safety variables will be essentially descriptive, and no testing is planned.
- Safety data in participants who do not belong to the safety population (eg, exposed but not randomized) will be provided separately.

Safety data will be assigned to study phase as following:

- Blinded Period, if the TEAE onset was between the first administration (Day 1) of any study intervention in the Blinded Period and the first administration of study intervention (SAR444727 Gel, 5%) in the Open-Label Period (scheduled Day 15 morning).

- Open-Label Period, if the TEAE onset was after the first administration of study intervention (SAR444727 Gel, 5%) in the Open-Label Period (scheduled Day 15 morning).

3.6.1 Extent of exposure

The extent of IMP exposure will be assessed by the duration of IMP exposure and compliance and will be summarized in the safety population for the double-blind period and the Open-label period.

Duration of IMP exposure

For each study period, duration of IMP exposure is defined as last IMP administration date – first IMP administration date + 1 days, regardless of unplanned intermittent discontinuation(s). If the date of the last dose of IMP is missing, the duration of IMP will be left as missing.

For each study period, duration of IMP exposure will be summarized quantitatively and categorically:

- Double-blind period: 1 day to \leq 7 days, $>$ 8 to $<$ 15 days, and \geq 15 days
- Open-label period: 15 days to \leq 29 days, $>$ 29 to \leq 43 days, and $>$ 43 days

Additionally, the cumulative duration of treatment exposure defined as the sum of the duration of treatment exposure over each study period for all participants will be provided.

Treatment compliance

Percentage of treatment compliance for a participant will be defined as the number of administrations/days that the participant was compliant divided by the total number of administrations/days that the participant was planned to take from the first administration of IMP up to the actual last administration of IMP.

Treatment compliance will be summarized over each study period, quantitatively and categorically: <80%, \geq 80% by treatment (SAR444727 Gel, 5% or placebo) and overall for the Open-label phase.

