1 INTRODUCTION

1.1 STUDY DESIGN

PRN473 is also known as SAR444727 and both terminologies are used in an interchangeable way in this document. For the reporting “SAR444727” will be used.

Study ACT17131 is a Phase 2a that consists of a randomized, double-blind, intra-patient placebo-controlled treatment period and an open-label uncontrolled treatment period.

The objective of the study is to evaluate the safety, tolerability, pharmacokinetics (PK) and preliminary efficacy of topically administered SAR444727 in up to 40 participants with mild to moderate atopic dermatitis (AD).

On Day 1 (Baseline) of the Blinded Period, 2 target lesions of 100 cm² area each with a difference no greater than 1 point in lesional Total Sign Score (TSS) are randomly assigned to treatment in an intra-participant 1:1 manner, with one lesion assigned to SAR444727 Gel 5% and the other to matching placebo (ie, same inactive ingredients). SAR444727 Gel 5% and matching placebo (ie, same inactive ingredients) are applied twice a day (BID, morning and evening) at a quantity of 2.5 mg/cm² to a 100 cm² area of each target lesion on Days 1-14 (Blinded Period). On Days 15-42 (Open-Label Period), participants are instructed to apply SAR444727 Gel, 5% BID to all AD-affected areas in a thin layer (excluding the scalp, palms, soles and genitals), and should continue to treat the assigned areas throughout the Open-label Period.

Participation will take approximately 13 weeks, including up to a 5-week screening period, a 6-week treatment period (2-week blinded and 4-week open label), end of study assessments 1 day after last dose, and a safety follow-up phone call 2 weeks after last dose.

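### The open-label exposure-duration categories in SAP 3.6.1 use study-day cut-offs for a duration counted within the period, so open-label exposures of 1 to 14 days have no category

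*SAP*

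**What the plan says.** SAP 3.6.1 (Extent of exposure) sets the rule: "For each study period, duration of IMP exposure is defined as last IMP administration date" minus first administration date plus 1, ignoring temporary interruptions. Duration is then to be summarised for each study period, both quantitatively and in categories.

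- Blinded period: the first category is "Double-blind period: 1 day to" 7 days inclusive, the second is over 8 to under 15 days, and the third is 15 days or more.
- Open-label period: the first category is "Open-label period: 15 days to" 29 days inclusive, the second is over 29 to 43 days inclusive, and the third is over 43 days.

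The same section provides a further measure, "the cumulative duration of treatment exposure defined as the sum of the duration of treatment exposure over each study period", for all participants.

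SAP 1.1 gives the period lengths: "a 6-week treatment period (2-week blinded and 4-week open label". It also gives the open-label dosing days: "On Days 15-42 (Open-Label Period), participants are instructed to apply SAR444727 Gel, 5% BID".

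The Schedule of Activities (Protocol 1.3) allows the Day 15 visit up to 2 days late and the Day 43 visit 2 days either way. Its footnote n places the last dose about 12 hours before the Day 43 visit. SAP Appendix 4 counts study days from the first blinded dose and uses Days 15, 29 and 43 as visit targets.

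**The concern.** The open-label categories and the duration they classify are on different scales. The duration restarts at 1 on the first open-label dose, while the limits 15, 29 and 43 are visit days counted from the first blinded dose. The categories therefore start 14 days too late for the quantity they describe.

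Exposure gives the context for the primary objective, which is safety and tolerability, and Protocol 9.4.4.4 commits to an exposure table. If the rule is programmed literally, the participants with the shortest open-label exposure appear in no row, and the category counts need not add up to the number exposed. If the programmer repairs the limits without a text change, the output departs from the approved SAP.

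**Working it through.** **Reproduce the planned lengths with the SAP's own formula** (last date − first date + 1):

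- Blinded, Days 1 to 14: 14 − 1 + 1 = 14 days, which matches 2 weeks.
- Open label, Days 15 to 42: 42 − 15 + 1 = 28 days, which matches 4 weeks.

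**Range for completers within the visit windows.** Assume that open-label dosing starts on the date of the Day 15 visit (Day 15 to 17). Assume also that the last dose is given the evening before the final visit (visit on Day 41 to 45, so last dose on Day 40 to 44).

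- Shortest: 40 − 17 + 1 = 24 days.
- Longest: 44 − 15 + 1 = 30 days.

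If the last dose instead fell on the day of the final visit, the range would be 25 to 31 days, with the same conclusion.

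**Put each whole-day duration through the printed categories.**

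| Period | Duration (days) | Category |
|---|---|---|
| Blinded | 1–7 | first |
| Blinded | 8 | none |
| Blinded | 9–14 (planned: 14) | second |
| Blinded | 15 or more | third; needs blinded dosing to continue to a late Day 15 visit (15–16 days) |
| Open label | 1–14 | none |
| Open label | 15–29 (planned: 28) | first |
| Open label | 30 | second |
| Open label | over 43 | third; not reachable within the windows |

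Of the durations 1 to 28, 14 have no open-label category and the other 14 fall in the first. After an on-time start, the unclassified durations correspond to a last open-label dose on study Days 15 to 28.

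The windows give 3 possible start days and 5 possible last-dose days, which is 15 combinations. Fourteen fall in the first category and one (Day 15 to Day 44, 30 days) in the second.

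To reach the third category, a participant who started on Day 15 would need 44 days. The last dose would then be on Day 15 + 44 − 1 = 58, after the scheduled Day 56 safety call.

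**Blinded period.** Study day and duration coincide here, so there is no scale error. The gap at 8 days comes only from the sign in "7 days, $>$ 8 to $<$ 15 days, and". The inequality signs around it are intact, so the text is probably as written, but a misread ≥ 8 cannot be excluded.

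**The case against.** *The open-label categories may have been meant to count from Day 1.* The 15-day lower limit would then make sense, and a 42-day completer would fall in the over 29 to 43 category. However, SAP 3.6.1 states the per-period definition explicitly, applies it again to the categorical summary, and lists cumulative exposure as a separate item. Even on the Day 1 reading, completers would share a category with anyone stopping on Days 30 to 41. The text would need changing either way.

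*Other outputs carry the information.* This stands, and it limits the point. SAP 3.6.1 also summarises duration quantitatively and compliance by period. SAP Appendix 2 counts participants who did not complete treatment, with the main reason, and lists permanent discontinuations. The safety analyses use the safety population, so no denominator changes.

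*Nothing says the categories are meant to show completion.* This also stands. A reader might infer that the trial cannot tell completers from early stoppers. The documents do not support that, because disposition is reported separately. It is true only that this one table does not make the distinction.

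*Counting durations is not counting participants.* This is correct. A reader might take 14 of 28 durations to mean that half the participants are lost. Only those who stop within their first 14 open-label days, or after exactly 8 blinded days, are affected.

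**Conclusion.** The open-label categories are wrong as written: durations of 1 to 14 days are unclassified, and nearly everyone else falls in one category. The blinded gap at exactly 8 days holds as printed, subject to checking the sign against the signed SAP.

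It would be too strong to say that neither upper open-label category can be reached. The over 29 to 43 category is reached at 30 days by an in-window completer; only the over 43 category is out of reach within the windows. It would also be too strong to extend the study-day error to the blinded period.

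The consequence is minor and confined to the categorical exposure table. The study enrols up to 40 participants and the documents give no discontinuation rate, so the number left out cannot be estimated and may be zero. The conclusion rests on the per-period definition. The 24-to-30-day range rests in addition on the visit windows and on a last dose the evening before the final visit.

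**What to change.** Replace the two category lines in SAP 3.6.1 with exhaustive categories, and state that days are counted from the first dose of the period concerned. For example:

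- Blinded: 1–7, 8–13 and ≥14 days.
- Open label: 1–14, 15–27 and ≥28 days.

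Every duration then falls in exactly one category, and the planned 14 and 28 days are separate from shorter exposures. Splits such as 8–14 and 15–28 would close the gaps but would still pool on-schedule completers with early stoppers.

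A limit of 28 days does not identify all completers, because those within the visit windows can have as few as 24 open-label days. Either take completion status from the disposition data, or lower the top limit to ≥24 days (with 15–23 as the middle category). Completion should not be inferred from the category alone.

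The cost is two lines of SAP text and the matching table shell. Data collection, design and treatment rules do not change.
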